The ePark study protocol: A decentralized trial of individual video-assisted cognitive behavioural therapy for depressive disorder in Parkinson's disease

[name]^{a,b,c,*}, [name]^{a,f,g}, [name]^{d,e}

^a The Norwegian Centre for Movement Disorders, Stavanger, Norway

^b Institute of Social Sciences, University of Stavanger, Stavanger, Norway

^c Center for Alcohol and Drug Research (KORFOR), Stavanger University Hospital, Stavanger, Norway

^d Department of Psychiatry, Maastricht University Medical Center, Maastricht, the Netherlands

^e School of Mental Health and Neuroscience, Maastricht University, Maastricht, the Netherlands

^f Department of Chemistry, Bioscience and Environmental Engineering, University of Stavanger, Stavanger, Norway

^g Department of Neurology, Stavanger University Hospital, Stavanger, Norway

1. Introduction

Parkinson's disease (PD) is the second most common neurodegenerative disorder, affecting 1.2 million Europeans [1]. The prevalence of PD in people over 60 is about 1%, increasing to 4% in people 80 years and older [2]. Although PD is defined as a motor disorder, non-motor symptoms including neuropsychiatric symptoms such as depression and anxiety, are frequent and disabling, with a major impact on quality of life, caregiver burden and healthcare costs [3].

Current pharmacological treatments for PD neuropsychiatric symptoms, including depression, are often unsatisfactory for several reasons, including frequent adverse effects of medication, elevated risk of polypharmacy, and limited availability for non-pharmacological treatment options [4,5]. Previously published RCTs have demonstrated large effect sizes of face-to-face, telephone administered and online CBT for depressive symptoms in PD [6–8]. Despite strong evidence that cognitive behavioural therapy (CBT) is effective and cost-efficient in reducing depressive symptoms in PD, few patients are offered this treatment [3, 6–10]. This is likely due in part to a shortage of CBT therapists at neurological outpatient clinics, particularly in rural areas, resulting in geographical differences in the availability of CBT treatment. This calls for the development of novel, evidence based online therapeutic strategies, which may significantly improve the lives of PD patients suffering from depressive symptoms.

1.1. Study aims and hypotheses

We will conduct a remote, randomized, delayed start trial, in order to.

- I. Assess the effectiveness of online, video-assisted cognitive behavioural therapy (eCBT) for depressive symptoms in patients with PD.
- II. Assess long-term outcomes, and predictors of long-term outcomes, of eCBT for depressive symptoms in PD.
- III. Explore the impact and clinical correlates of eCBT working alliances in patients with PD.

For the first aim, we hypothesize that.

- i. eCBT will reduce the self-reported severity of depressive symptoms in patients with PD, as compared to patients in a control group receiving treatment as usual (TAU).
- ii. eCBT will reduce the observed severity of depressive symptoms in patients with PD, as compared to patients in a control group receiving TAU.
- iii. eCBT will improve self-reported health related quality of life in patients with PD, as compared to patients in a control group receiving TAU.

For the second aim, we hypothesize.

* Corresponding author. The Norwegian Centre for Movement Disorders, Stavanger University Hospital, [name].
E-mail address: [contact] ([name]).

- iv. Participants in group A (early eCBT) and group B (late eCBT) will have comparable depression scores 14 weeks following the eCBT intervention.
- v. A poorer long-term treatment response to eCBT for depressive symptoms is predicted by more severe self-reported comorbid symptoms of anxiety and impulse control disorders at baseline.
- vi. A better long-term treatment response to eCBT for depressive symptoms is associated with greater change in self-reported comorbid symptoms of anxiety and impulse control disorders at the time of treatment completion.

For the third aim, we hypothesize.

- vii. The quality of the therapeutic working alliance, as measured by patient self-report, as well as adherence levels, will significantly predict change in self-reported depression scores.
- viii. Patients self-reported working alliance scores will significantly predict the acceptability of eCBT, as defined by patient reported experience measures.

2. Methods

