2.5. Sample size and feasibility

A priori power calculations was performed using G*Power 3.1.9.2 [15,16]. Power analysis is based on power calculation for *t*-test, and it serves as a lower bound estimate of power as it applies as long as each patient has at least two measurements. Multiple observations per subject will increase the power and eliminate the impact of possible missing

observations. The study is powered to identify a mean difference in HADS-D score of 1.98 points, with $\alpha = 0.05$, power set to 80%, and a predicted effect size of Cohen's $d = 0.80$. Based on these calculations, the required number of participants is 84 (42 per group). Including $N = 60$ participants per group will allow for up to 30% dropout from the study, while retaining sufficient statistical power. Based on the large effect sizes observed in other RCTs investigating CBT for depression in PD [6–8], we expect the effect size to be larger and the drop out to be lower ($\approx 10\%$). Participants whom decide to leave the study prematurely will not be replaced by new participants, and their data will be included in the main analysis according to an intention-to-treat principle.

There is an estimated 7000 patients with PD in Norway, of whom about 3500 are members of the patient organization the Norwegian PD Association. With a conservative frequency of 30%, depressive symptoms would affect approximately >2000 Norwegian PD patients in general, and >1000 of the members of the Norwegian PD Association. While access to computers and adequate internet bandwidth is largely ubiquitous in a Norwegian setting, familiarity with online platforms and video-conferencing could still limit recruitment for this study. However, a recent nationwide survey using similar data-gathering tools demonstrated that a large proportion of the PD community manages to use the technologies employed in this study [17]. Thus recruitment of $N = 120$ participants for this study is thus considered feasible.

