Also, due to the online design of this study several additional security precautions will be in place before initiation of the study. These include procedures of how to address acute medical situations, such as suicidal ideation or acute psychosis. For each participants a security card, with emergency contacts, contact information to nearby emergency services, ambulatory mental health services and general practitioner, will be prepared before the initiation of interventions. These data will be gathered during the second screening/baseline assessment. In case of increased suicidal ideation during the course of treatment, clinicians will follow local clinical guidelines for increased suicidal ideation. Clinicians are free to admit patients to acute outpatient or inpatient care in case of acute suicidal ideation. Participants with acute suicidal ideation will be excluded from the study.

3. Analysis plan

All analyses in this project will be performed using IBM SPSS Statistics version 26.0.0.1 or R 4.2.1, or more recent versions if available. An alpha-level of 0.05 will be used to indicate statistical significance. Descriptive statistics will be summarized using means, median, standard

deviations and ranges for numerical variables, and frequencies and percentages for categorical variables. Relevant univariate and multivariate analytic strategies will be used to test hypotheses h^i - h^{viii} .

For aim 1 (h^i - h^{iii}), linear mixed model analysis (LMM) with maximum likelihood estimation, based on an intent-to-treat protocol, will be used to gauge the between-group differences from baseline to the 14 week follow up. LMM will limit the impact of type 1 errors, and fully use the available data (in case of missing data). A random intercept for each participant and random slope will be included if they enhanced the model fit (evaluated using Akaike’s information criteria and Schwarz’s Bayesian criterion). In these analyses, a sum score from the primary and secondary outcomes will be used as dependent variables, and with significant covariates including treatment group, age, gender, duration of PD, and medication use. Medication use will be converted to levodopa equivalent dosages, using previously described procedures [18]. This analysis will be repeated using a per-protocol approach, where only completers (completed all core sessions) are included. Effect sizes will be calculated using Cohen’s d , with pooled pre- and post-SD adjustment for sample size.

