For aim 2 and 3, linear regression analysis will be used to estimate group differences in depression scores at the end of the study (h^{iv}), and the association between working alliance and acceptability (h^{viii}). Independent variables include, gender, treatment group, age, duration of PD and medication use. Predictors for treatment effect will be investigated using (h^v , h^{vi} and h^{vii}) LMM, as described above.

4. Discussion

CBT is the first line treatment of choice for depression in the general population [19], and a number of studies have confirmed its effectiveness in patients with PD [9,20,21]. The limited availability of this treatment, especially in specialized treatment centres, such as movement disorder clinics, motivated earlier trials to conduct CBT remotely, e.g. via telephone [6,8,22,23]. However, this is the first trial using video-assisted online CBT in this population. The great advantage of video-assisted CBT over telephone-administered CBT is the fact that patient and therapist are able to see each other, including facial expressions and body language, which may be beneficial for the working alliance. However, no information on how working alliance is affected by online-therapy exists in patients with PD.

This is the first RCT to evaluate the effectiveness of online video-assisted CBT for depressive symptoms in people with PD and to study working alliance in this online setting. By following a fully online design for gathering informed consent, assessment and treatment delivery, we are able to include patients nation-wide. This will increase the clinical applicability of our findings, and allows for future implementation in sparsely populated settings where clinical services may be physically located far away from the patient.

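### Hypothesis iv predicts comparable early and late outcomes, but the assigned difference regression at alpha 0.05 has no criterion for comparability, omits the baseline score and uses a different time point

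*Protocol*

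**What the plan says.** Section 1.1 of the protocol states, as hypothesis iv under the second aim, that groups A (early eCBT) and B (late eCBT) "will have comparable depression scores 14 weeks following the eCBT intervention". Nowhere does the protocol say how close the scores must be to count as comparable.

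Section 3 (Analysis plan) sets a general rule: "An alpha-level of 0.05 will be used to indicate statistical significance". It adds that "Relevant univariate and multivariate analytic strategies will be used to test hypotheses" i to viii, which includes hypothesis iv. For hypothesis iv the method is that "linear regression analysis will be used to estimate group differences in depression scores at the end of the study". The covariates are given once, for hypotheses iv and viii together: "Independent variables include, gender, treatment group, age, duration of PD and medication use". Baseline depression is not among them, although Table 2 has HADS completed at baseline and at weeks 14, 28 and 42.

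The only sample size calculation, in section 2.5, is for detecting a HADS-D difference of 1.98 points between the arms. It is not a calculation for showing that they are alike.

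**The concern.** Hypothesis iv claims that no relevant difference exists. The model assigned to it can show that a difference exists. If it does not, the result is inconclusive unless the confidence interval is short compared with some stated tolerance, and none is stated. The hypothesis, the method and the decision level are all in the protocol, and they do not fit together.

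At stake is the only between-arm statement under the second aim. With alpha 0.05 as the only criterion on offer, a finding of no significant difference could be reported as agreement with the hypothesis. That becomes easier as participants are lost. Two further weaknesses affect the same analysis: it gives up precision available from the baseline score, and section 1.1 and section 3 do not describe the same comparison in time.

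**Working it through.** **1. The plan's own figure.** Section 2.5 gives d = 0.80, alpha 0.05, "power set to 80" percent, a t-test, and 42 per group. A two-sided t-test with those inputs needs 26 per group (21 if one-sided). The figure of 42 is what two-sided 95% power requires (power at 42 per group is 95.2%), so 84 does not reproduce at the stated power. That is a separate matter. Here 42 serves only as a group size.

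**2. Inputs.**
- SD: 1.98/0.80 = 2.475 HADS-D points (section 2.5), assumed to apply to follow-up scores.
- Group sizes: 60 × 0.70 = 42 at the 30% dropout allowed for, and 60 × 0.90 = 54 at the roughly 10% expected (section 2.5).
- Outcome: HADS-D is assumed, because hypothesis iv does not name its depression score.
- Sidedness is not stated; two-sided is assumed.

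**3. Precision without baseline adjustment.** SE = 2.475 × √(2/n); half-width = t × SE with 2n − 2 degrees of freedom.
- n = 42: SE = 0.540; half-width 1.07 (95%) and 0.90 (90%).
- n = 54: SE = 0.476; half-width 0.94 (95%) and 0.79 (90%).

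**4. Chance of a non-significant result** (noncentral t, noncentrality = true difference/SE):

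| Per arm | True 0.5 | True 1.0 | True 1.5 | True 1.98 |
|---|---|---|---|---|
| 30 (illustrative) | 88% | 66% | 36% | 14% |
| 42 | 85% | 55% | 22% | 5% |
| 54 | 82% | 45% | 12% | 2% |
| 60 | 81% | 41% | 9% | 1% |

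Fewer participants make non-significance more likely in every column. At an illustrative SD of 3.0, which is not in the documents, the figures for a true 1.0 point are 67% (42 per arm) and 60% (54 per arm).

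**5. What a proper comparability test could do.** Two one-sided tests at 5% conclude comparability when the 90% interval lies inside ± margin. At zero true difference, power is about 2Φ(margin/SE − t) − 1. For a margin of 1.5 and n = 42: 1.5/0.540 = 2.78; minus 1.66 gives about 1.11; power about 73%. Integrating over the estimated SD gives:

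| Margin | 42 per arm | 54 per arm |
|---|---|---|
| 1.0 | 16% | 34% |
| 1.5 | 73% | 86% |
| 1.98 | 95% | 99% |

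**6. Baseline adjustment.** If baseline and follow-up correlate at 0.5 (an assumption), residual variance falls by 0.5² = 25%. Power for the 1.5-point margin then rises to 88% (42 per arm) and 95% (54 per arm).

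**7. Time point.** By sections 2.6 and 2.7, arm A is treated over the first 13 weeks or so, and arm B starts after the week-14 assessment on the same schedule.

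| | Treatment window ends | 14 weeks later | Week 42 is |
|---|---|---|---|
| Arm A | about week 14 | about week 28 | about 28 weeks after |
| Arm B | about week 28 | about week 42 | about 14 weeks after |

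The hypothesis therefore compares week 28 in arm A with week 42 in arm B. The regression at the end of the study compares week 42 in both.

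**The case against.** The strongest reply is that the faulty decision rule is inferred. A reader might conclude that the protocol equates p > 0.05 with comparability. It never says so, and its verb for this regression is to estimate, which would allow a confidence-interval reading. That stands. But without a tolerance there is nothing to judge the interval against, and section 3 says that hypothesis iv is to be tested.

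A second reply is that a margin for a second-aim hypothesis can be left to the SAP, which is not at hand. A missing margin alone would indeed be no finding. The point here is that the protocol itself pairs a claim of likeness with a test of difference.

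Third, large differences would rarely be missed: about 2% to 5% for 1.98 points. That is correct at the implied SD. It would settle the matter only if 1.98 were the agreed tolerance, and the protocol does not say that it is.

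Four stronger readings should be resisted:
- **Only those seen at the last visit are analysed.** Section 3 gives no such rule for hypothesis iv, and section 2.5 keeps leavers' data in the main analysis by intention to treat.
- **Omitting baseline biases the comparison.** Randomization protects against that, apart from chance imbalance and dropout, so the loss is mainly precision. The covariate list may also not be exhaustive.
- **A trivial but significant difference would refute the hypothesis.** Unadjusted significance needs an observed difference of about 0.94 to 1.07 points, roughly half the design effect.
- **Hypothesis iv is meant to show that waiting does no harm.** The protocol does not say this; its discussion justifies the delayed start by recruitment, ethics and control for natural remission.

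**Conclusion.** The point holds in this form: the regression at alpha 0.05 cannot support a prediction of comparable scores, because the protocol gives no criterion for comparability. At SD 2.475, a true difference of 1.0 point, about half the effect the trial is designed around, would go undetected in about 45% of trials at the expected dropout and 55% at the maximum allowed. The risk concerns differences of about that size, or a larger SD or heavier loss, and not differences near 1.98 points.

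The missing criterion is the main defect. The absent baseline score is a lesser matter of efficiency. The mismatch in time point is a plain inconsistency between sections 1.1 and 3, and any test of the hypothesis is ill defined until it is settled. The figures assume HADS-D as the outcome, two-sided testing, no covariate adjustment and the SD implied by section 2.5. The hypothesis is not part of the first aim, so this should be corrected but does not threaten the main comparison.

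**What to change.** - **Criterion.** State that hypothesis iv is supported if the 90% confidence interval for the A − B difference lies within a margin in HADS-D points. Justify the margin before data are seen and keep it clearly below 1.98, since a margin equal to the whole design effect would be too lenient. As an illustration, 1.5 points gives about 73% to 86% unadjusted power; 1.0 point gives only 16% to 34%.
- **Alternative.** If no margin can be justified, restate hypothesis iv as an estimate of the difference with a 95% confidence interval, and drop the word comparable.
- **Covariate.** Add baseline HADS-D to the regression for hypothesis iv.
- **Time point.** Reconcile sections 1.1 and 3: say whether the arms are compared at equal time since treatment (week 28 for A, week 42 for B) or both at week 42, and use the same wording in both places.

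The cost is a change of wording and agreement on a margin; no visits, measures or participants are added. The downside is that the comparison may have to be reported as inconclusive.

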2.1. Study setting

This study is a decentralized national trial, recruiting from both clinical settings (i.e. neurological clinics) and allowing for self-referral by PD patients from the general population. The project is organized by the Norwegian Centre for Movement Disorders, Stavanger University Hospital, Norway.

2.2. Study design

This study is an online, randomized, delayed start trial of the effectiveness of eCBT for PD patients with depressive symptoms. N = 120 PD patients with depressive symptoms will be recruited from outpatient clinics and via self-referral in Norway, and randomized into two arms: (A) immediate 10-weeks eCBT with concurrent TAU and (B) a delayed start (14 weeks) of eCBT with TAU alone. Patients will be assessed at baseline before allocation to a specific treatment arm, with follow-up evaluations after 14, 28 and 42 weeks. See Fig. 1 for the study flow.

2.3. Recruitment procedures

A recruitment and information website will be established for the study. As well as being a recruitment portal, this website will also contain instructions on how to complete online self-report measures, and how to use the videoconference system "Join.nhn.no". The study will recruit participants in collaboration with 1) neurological clinics in all four health regions of Norway, and 2) the national user organization for people with PD in Norway (Norwegian PD Association, NPDA). The role of collaborating clinics and the NPDA is to raise awareness of the study, to inform potential participants and direct them to the bespoke study web-page. Neither the clinics nor NPDA will be required to perform any assessment of potential participants.

Potential study participants will be directed to the study website, where they will be informed about the design and goals of the study. Those visiting the website will be informed that participation is voluntary, and that they have the right to withdraw from the study at any time without the risk of repercussions or prejudice. Participants interested in joining the study are then guided to an online platform (on the TSD-platform, see details later in the protocol) to read and sign an informed consent form. After signing an informed consent form, all participants will complete an online screening procedure, consisting of a short, structured questionnaire, and self-report measures for depression and anxiety. The screening procedure includes the following: a) Screening form addressing demographic information, medical history

and current symptoms, and subjective cognitive complaints; and b) Hospital Anxiety and Depression Scale (HADS). A score of >7 on HADS depression items (HADS-D) will be considered a positive screening for depression [11]. This cut-off is in line with previous studies using HADS with PD [12]. After completion of the screening procedure, participants meeting the central *a priori* inclusion criteria (see section 2.4) will be invited to a second screening after one to two weeks. Patients will also be informed that they may use the time until the second screening session to reflect on whether they want to participate in the study.

During the second screening process, participants will undergo a more comprehensive evaluation of their medical history, medication use, clinical status, cognitive functioning, and severity of neuropsychiatric symptoms. This screening will be performed by a trained study nurse over "Join.nhn.no". After the second screening, patient records will be evaluated by an interdisciplinary team (nurse and senior consultant clinical psychologist) against the criteria for major depressive disorder (MDD). The diagnosis of MDD will be assessed using the provisional diagnostic criteria for depression in PD and the MDD criteria from the Diagnostic and Statistical Manual for Mental Disorders, 5th edition [13,14]. Participants will be considered for inclusion in the study according to the core inclusion and exclusion criteria (see 2.4 study eligibility criteria). Included patients will be trained in the use of the TSD-platform while completing a set of self-report measures as part of their baseline assessment. Excluded patients will be referred on to appropriate treatment services near their area of living. For all included participants, information will be passed on to the treating neurologist and general practitioner, detailing the aims of the study, information of diagnostic assessments of PD, and information of medication limitations during the trial.

